10.0 Drugs and Devices

10.1 * DRUGS AND/OR BIOLOGICS: Are you **STUDYING any drugs and/or biologics that are either approved or unapproved: (REQUIRED)**

Yes No

If you have questions about FDA requirements for drug or device research, you can send an [email](#) to request a consult.

10.2 LIST THE DRUGS OR BIOLOGICS: List the drugs or biologics that will be studied. In the drug details screen you will be asked questions such as:

- Whether the drug or biologic is FDA approved
- If the drug or biologic will be provided at no cost
- If an IND is necessary, the IND number, and who holds the IND
- If the drug or biologic is FDA approved and an IND is not required, the rationale for the decision
- If the **Investigational Drug Service (IDS)** is dispensing the drug or biologic (required unless a **waiver** is obtained from the IDS)

Please see the **UCSF IRB website** for more details about the use of drugs and biologics in research, including the **IND Decision Worksheet**. Verification of IND numbers: If the sponsor's protocol does not list the IND number, you must submit documentation from the sponsor or FDA identifying the IND number for this study. Attach this documentation in the Other Study Documents section of the Initial Review Submission Packet. **If you have any correspondence from the FDA or sponsor regarding this drug or biologic, please attach it to the application.**

View Details	Drug Name	FDA Approved	A new drug or a new use of an already approved drug:	IND Number																																																																
	Trade Drug NALTREXONE Name: HYDROCHLORIDE Generic Drug NALTREXONE Name: HYDROCHLORIDE Investigational Drug Name:	Yes	Yes																																																																	

 
 Trade Drug Name:	NALTREXONE HYDROCHLORIDE	
 
 Generic Drug Name:	NALTREXONE HYDROCHLORIDE	
 
 Investigational Drug Name:		
 
 Identify the name of the manufacturer or source of investigational drug/biologic:	ReVia	
 
 Is the drug supplied at no cost?	No	
 
 Is the Drug FDA Approved:	Yes	
 
 Is this a new drug or a new use of an already approved drug	Yes	
 
 Is an IND necessary	No	
 
 IND Number		
 
 Who holds the IND:	N/A	
 
 IND details:		
 
 If FDA Approved and an IND is not required, Please provide a rationale for exemption:	 
This study meets exemption criteria under 21CFR312.2: the investigator is not intending to report the study in support of a new indication or change in advertising; there is no significant increase in risk in this study population and it uses the same dose and route as FDA-approved; the study will comply with IRB and informed consent requirements; and the investigator has no disqualifications. We have submitted the UCSF IND Decision worksheet in other study documents.
 	
 
 Are you currently using this IND in another research project?	No	
 
 If yes, list the IRB Number(s):		
 
 Will the investigational pharmacy be dispensing?	No	
 
 If the source is not a FDA licensed facility, provide details regarding the purity, quality, stability and sterility of the investigational drug/biologic:		
 
					Trade Drug Name:	NALTREXONE HYDROCHLORIDE			Generic Drug Name:	NALTREXONE HYDROCHLORIDE			Investigational Drug Name:				Identify the name of the manufacturer or source of investigational drug/biologic:	ReVia			Is the drug supplied at no cost?	No			Is the Drug FDA Approved:	Yes			Is this a new drug or a new use of an already approved drug	Yes			Is an IND necessary	No			IND Number				Who holds the IND:	N/A			IND details:				If FDA Approved and an IND is not required, Please provide a rationale for exemption:	
This study meets exemption criteria under 21CFR312.2: the investigator is not intending to report the study in support of a new indication or change in advertising; there is no significant increase in risk in this study population and it uses the same dose and route as FDA-approved; the study will comply with IRB and informed consent requirements; and the investigator has no disqualifications. We have submitted the UCSF IND Decision worksheet in other study documents.
			Are you currently using this IND in another research project?	No			If yes, list the IRB Number(s):				Will the investigational pharmacy be dispensing?	No			If the source is not a FDA licensed facility, provide details regarding the purity, quality, stability and sterility of the investigational drug/biologic:			
Trade Drug Name:	NALTREXONE HYDROCHLORIDE																																																																			
Generic Drug Name:	NALTREXONE HYDROCHLORIDE																																																																			
Investigational Drug Name:																																																																				
Identify the name of the manufacturer or source of investigational drug/biologic:	ReVia																																																																			
Is the drug supplied at no cost?	No																																																																			
Is the Drug FDA Approved:	Yes																																																																			
Is this a new drug or a new use of an already approved drug	Yes																																																																			
Is an IND necessary	No																																																																			
IND Number																																																																				
Who holds the IND:	N/A																																																																			
IND details:																																																																				
If FDA Approved and an IND is not required, Please provide a rationale for exemption:	
This study meets exemption criteria under 21CFR312.2: the investigator is not intending to report the study in support of a new indication or change in advertising; there is no significant increase in risk in this study population and it uses the same dose and route as FDA-approved; the study will comply with IRB and informed consent requirements; and the investigator has no disqualifications. We have submitted the UCSF IND Decision worksheet in other study documents.
																																																																			
Are you currently using this IND in another research project?	No																																																																			
If yes, list the IRB Number(s):																																																																				
Will the investigational pharmacy be dispensing?	No																																																																			
If the source is not a FDA licensed facility, provide details regarding the purity, quality, stability and sterility of the investigational drug/biologic:																																																																				

10.3 * MEDICAL DEVICES: Are you **STUDYING any medical devices, in vitro diagnostics, or assays that are either approved or unapproved:(REQUIRED)**

Yes No

If you have questions about FDA requirements for drug or device research, you can send an [email](#) to request a consult.

10.6 * EXPANDED ACCESS: Is this an expanded access or compassionate use protocol, meaning the primary purpose is to diagnose, monitor or treat a patient's condition, rather than the collection of safety and efficacy data of the experimental agent: (REQUIRED)

Yes No

11.0 Sample Size and Eligibility Criteria

11.1 ENROLLMENT TARGET: How many people will you enroll:

60

If there are multiple participant groups, indicate how many people will be in each group:

The ION+EMI study will enroll 60 participants in the double-blinded placebo controlled clinical trial where 40 participants will receive Intermittent Oral Naltrexone and 20 participants will receive placebo.

11.3 SAMPLE SIZE JUSTIFICATION: Explain how and why the number of people was chosen. For multi-site studies, this is referring to the number that will be enrolled across all sites:

For the phase 2b clinical trial, a sample size of 60 was selected to provide 80% power in 2-sided tests with a type-I error rate of 5% to detect between a 18-22% reduction of meth use among the ION arm, compared to placebo, in ITT and sub-group analyses. We hypothesized on pharmacologic grounds that oral naltrexone will reach full efficacy against meth use almost immediately; accordingly we expect treatment-control differences to be approximately constant over the 12 weeks of the trial. Based on the prior trial (93% retention), we estimate that 90% of participants will be retained at 12 weeks. Under these assumptions, the minimum detectable effects for our outcomes are calculated as follows:

Specific Aim 1: *To determine the efficacy of ION vs. placebo in reducing meth use, as determined by the proportion of meth-positive sweat patch tests.* As in our prior trial, a GEE Poisson model with robust standard errors will be used to compare weekly urine test results by treatment assignment; this provides easier-to-interpret risk-ratios²¹⁸ rather than odds-ratios. The treatment effect of ION vs. placebo will be modeled as linearly increasing and summarized by the between-group difference in means at 12 weeks, net of any baseline difference. *Minimum Detectable Effects (MDEs) with sample size:* Based on the prior trial (93% retention with an 8-week follow-up), we estimate that 90% of participants will be retained at 12 weeks, and within-subject correlation will be 0.45. Under these assumptions, the study sample of 60 participants will have 80% power in 2-sided tests with a type-I error rate of 5% to detect net between-group differences in the reduction in urine positivity of ~24 percentage points, equivalent to a relative rate reduction of 32%. We have observed similar reductions on meth use in ITT and sub-group analyses in prior trials.¹⁰⁹ Therefore, we believe that the reductions in meth use we are powered to detect in this aim are reasonable to anticipate. *In sensitivity analyses,* we will also evaluate between-group differences on changes in: 1) any meth-positive samples or self-report of meth use in timeline follow back; and 2) meth positivity from self-report only. Concordance of the urine testing, and self-reported measures will be examined using weighted Kappa and correlations. We recognize that meth use is a stigmatized behavior that may be underreported. Hence, in the event of discrepancies between urine test results and timeline follow back data on meth use, we will treat the urine test results as the gold standard. *Additionally, we will analyze participant's perception of whether the EMI prompts had effects on various HBM constructs and explore whether these moderate treatment effects on meth use.*^{119,120}

Specific Aim 2: *To determine the efficacy of ION vs. placebo in reducing meth-associated sexual risk behaviors.* We will use GEE Poisson models with robust standard errors to assess evidence that the intervention reduces HIV risk behaviors, including number of sex partners,

number of sex partners with whom meth is used and episodes of condomless sex with serodiscordant partners. *MDEs:* Using data from our prior trial on baseline means, within-subject correlation, and over-dispersion, we estimate that the study sample of 60 participants will have 80% power to detect ~46% net reductions in the numbers of sexual partners. In our Project iN study, we have observed statistically significant reductions on sexual risk outcomes ranging between 85%-89% among the treatment arm, compared to placebo.¹⁰⁹ Therefore, given the results from the prior trial, we believe that the reductions we are powered to detect in this aim are reasonable to anticipate. *In sensitivity analyses*, we will examine how PrEP use and viral suppression status of participants and their partners (partner data assessed via self-reported egocentric data collection from participants)²¹² modify treatment effects on sexual risk behaviors. We will also examine whether there is evidence of effect modification depending on whether both the study participant and partner, the participant only, the partner only, or neither the participant nor the partner used a biomedical HIV prevention tool (PrEP or ART).²¹²

Specific Aim 3: To determine the efficacy of ION vs. placebo in increasing PrEP adherence among HIV-negative participants and ART adherence among participants living with HIV, as measured by serum drug-levels and viral suppression rates. We will use GEE Poisson models with robust standard errors to assess evidence that the intervention increases PrEP and ART adherence. *MDEs:* Using the assumptions for loss to follow-up from Project iN for Aim 1, we estimate that the study sample with 60 participants will have 80% power to detect 10-19 percentage point increases in PrEP/ART adherence, depending on within-subject correlations and adherence levels in the reference group.^{126,220}

The sample size of 60 participants is the minimum number required to have sufficient power to determine the MDEs of intermittent naltrexone in reducing meth use for the phase 2b study.

11.4 * PARTICIPANT AGE RANGE: Eligible age ranges: (REQUIRED)

- 0-6 years
- 7-12 years
- 13-17 years
- 18-64 years
- 65+

11.5 * STUDY POPULATIONS: Data will be collected from or about the following types of people (check all that apply): (REQUIRED)

- Inpatients
- Outpatients
- Family members or caregivers
- Providers
- People who have a condition but who are not being seen as patients
- Healthy volunteers
- Students
- Staff of UCSF or affiliated institutions
- None of the above

11.6 * SPECIAL SUBJECT GROUPS: Check the populations that may be enrolled: (REQUIRED)

- Children / Minors
- Adult subjects unable to consent for themselves
- Adult subjects unable to consent for themselves (emergency setting)
- Subjects with diminished capacity to consent
- Subjects unable to read, speak or understand English
- Pregnant women
- Fetuses
- Neonates

Prisoners
 Economically or educationally disadvantaged persons
 None of the above

11.7 INCLUSION CRITERIA: Briefly describe the population(s) that will be involved in this study. Include anyone that data will be collected from or about (e.g. patients, healthy controls, caregivers, providers, administrators, students, parents, family members, etc.):

Inclusion Criteria: 1) cisgender male (male gender and sex assigned at birth); 2) age 18-70 years* (naltrexone's tolerability and safety has been demonstrated among older adults up to age 70^{166,167}); 3) self-reported condomless anal sex with men or missing PrEP or ART doses due to meth use in the prior three months while under the influence of meth; 4) self-reported meth use at least weekly; 5) positive meth sample via sweat patch or urine testing during screening; 6) mild, moderate, and severe meth use disorder as determined by DSM-V-SCID criteria; 7) interested in reducing meth use; 8) no current acute illness requiring prolonged medical care; 9) no chronic illness that is likely to progress clinically during trial; 10) able and willing to provide informed consent and adhere to visit schedule; 11) current CD4 count \geq 200 cells/mm³; or CD4 count of 100-199 cells/mm³ and HIV viral load $<$ 200 copies/mL (if living with HIV); 12) baseline CBC, total protein, albumin, glucose, alkaline phosphatase, creatinine, BUN, and electrolytes without clinically significant abnormalities as determined by study clinician in conjunction with symptoms, physical exam, and medical history.

11.8 EXCLUSION CRITERIA: List any exclusion criteria (e.g. reasons why someone would not be included in the study):

Exclusion Criteria: 1) any psychiatric (e.g., depression with suicidal ideation) or medical condition that would preclude safe participation; 2) known allergy or prior adverse reaction to naltrexone; 3) current use of any opioids or a known medical condition which currently requires or may likely require opioid analgesics; 4) opioid-positive urine test at screen/enrollment visits (naltrexone can induce opioid withdrawal); 5) moderate or severe liver disease (AST, ALT, or total bilirubin \geq 3 times upper limit of normal); 6) impaired renal function (creatinine clearance $<$ 60 ml /min); 7) currently participating in another intervention research study with potential overlap; 8) severe alcohol use disorder as determined by DSM-V SCID criteria; 9) any condition that, in the PI and/or study clinician's judgment interferes with safe participation or adherence to study procedures.

11.9 * RESEARCH CONDUCTED ON PATIENT CARE WARDS: Do any study activities take place on any patient care units including inpatient wards, peri- or post-operative care units, operating rooms, or in the Emergency Department at UCSF Health medical facilities: **(REQUIRED)**

Yes No

11.11 * EMERGENCY DEPARTMENT: Does your protocol or study involve any of the following patient related activities in the emergency department (e.g. subject identification, recruitment, consent, blood draws, specimen retrieval, involvement of ED staff (nursing, tech, and/or physician), or any other ED based procedures): **(REQUIRED)**

Yes No

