Specific Aim 1: *To determine the efficacy of ION vs. placebo in reducing meth use, as determined by the proportion of meth-positive urine tests.* As in our prior trial, a GEE Poisson model with robust standard errors will be used to compare weekly urine test results by treatment assignment; this provides easier-to-interpret risk-ratios²¹⁸ rather than odds-ratios. The treatment effect of ION vs. placebo will be modeled as linearly increasing and summarized by the between-group difference in means at 12 weeks, net of any baseline difference. *Minimum Detectable Effects (MDEs) with sample size:* Based on the prior trial (93% retention with an 8-week follow-up), we estimate that 80% of participants will be retained at 12 weeks, and within-subject correlation will be 0.45. Under these assumptions, the study sample will have 80% power in 2-sided tests with a type-I error rate of 5% to detect net between-group differences in the reduction in sweat patch positivity of ~14.5 percentage points. In the Project iN study, we have observed reductions on meth use between 18%-22% among the ION arm, compared to placebo, in ITT and sub-group analyses.¹⁰⁹ Therefore, we believe that the reductions in meth use we are powered to detect in this aim are reasonable to anticipate. *In sensitivity analyses*, we will also evaluate between-group differences on changes in: 1) any meth-positive samples or self-report of meth use in timeline follow back; and 2) meth positivity from self-report only. Concordance of the urine testing, and self-reported measures will be examined using weighted Kappa and correlations. We recognize that meth use is a stigmatized behavior that may be underreported. Hence, in the event of discrepancies between urine results and timeline follow back data on meth use, we will treat the urine test results as the gold standard. *Additionally, we will analyze participant's perception of whether the EMI prompts had effects on various HBM constructs and explore whether these moderate treatment effects on meth use.*^{119,120}

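### Section 11.3 claims 80% power for an 18-22% reduction in meth use, but the plan's own 80%-power detectable effect is about 24 points (32% relative); power at 18-22% is roughly 35-49%, or 48-64% with a constant, baseline-adjusted effect

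*Protocol*

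**What the plan says.** The documents make several statements about what Aim 1 can detect.

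- **Protocol 11.3, opening paragraph.** Sixty participants were selected "to provide 80% power in 2-sided tests with a type-I error rate of 5% to detect between a 18-22% reduction of meth use" on naltrexone compared with placebo. The effect is assumed immediate: "accordingly we expect treatment-control differences to be approximately constant over the 12 weeks of the trial". Retention is taken as 90%.
- **Protocol 11.3, Aim 1.** The aim is worded "as determined by the proportion of meth-positive sweat patch tests", although the analysis described is of weekly urine tests. "The treatment effect of ION vs. placebo will be modeled as linearly increasing" and summarised at week 12 net of baseline. With 90% retention and within-subject correlation 0.45, the detectable effect at 80% power is a "reduction in urine positivity of ~24 percentage points, equivalent to a relative rate reduction of 32" per cent. This is described as similar to earlier results.
- **SAP, Aim 1.** The same 24 points and 32%, the same linear model, 90% retention and the same appeal to earlier results, but for 54 participants.
- **Protocol 8.13, Aim 1.** The aim is defined by urine tests, but "we estimate that 80% of participants will be retained at 12 weeks" and the power is "to detect net between-group differences in the reduction in sweat patch positivity of ~14.5 percentage points". On the pilot: "we have observed reductions on meth use between 18%-22% among the ION arm, compared to placebo, in ITT and sub-group analyses".
- **Protocol 8.5.** The pilot risk ratio for meth use was 0.82 by intention to treat, not statistically significant. In the subgroup using at least one day per week, the risk ratio for meth-using days was 0.78.

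**The concern.** A design with 80% power at a 32% relative reduction must have less than 80% power at 18-22%. Section 11.3 nevertheless claims 80% for both. Calling 32% similar to the pilot's 18% and 22% has the same fault.

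The supporting assumptions also disagree: constant against linearly increasing effect, urine against sweat patch, 80% against 90% retention. Section 11.3 gives this calculation as the reason for enrolling 60, so a reader cannot tell what effect the trial can detect. A null result could be misread as evidence against a pilot-sized effect that the trial had only a modest chance of finding.

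**Working it through.** **Inputs from the documents.** Two-sided alpha 0.05 and 80% power, so z = 1.96 + 0.84 = 2.80. Allocation 40:20; at 90% retention 36 and 18 (total 54, as in the SAP), at 80% retention 32 and 16. Within-subject correlation 0.45. Urine tests at enrollment and weekly for 12 weeks.

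**Derived input.** No placebo positivity rate is stated. 24 points being 32% relative implies 24/0.32 = 75%. Rounding allows 23.5/0.325 = 72% to 24.5/0.315 = 78%.

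**Formula.** With placebo rate p0 and naltrexone rate p1,

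Var = f × [p0(1−p0)/n0 + p1(1−p1)/n1], MDE = 2.80 × √Var, power = Φ(d/√Var − 1.96).

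The factor f depends on the effect shape, with exchangeable correlation 0.45:

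- Linear effect, weeks 0-12, contrast at week 12 net of baseline: f = 0.55 × 144/182 = 0.435 (182 is the sum of squares of 0 to 12 about their mean).
- Constant effect, mean of 12 tests, no baseline adjustment: f = (1 + 11 × 0.45)/12 = 0.496.
- Constant effect, baseline-adjusted: f = 0.496 − 0.45² = 0.293.
- Constant effect, observed baseline difference subtracted: f = 0.496 + 1 − 2 × 0.45 = 0.596.

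**Reproducing the stated figure.** Linear model, p0 = 0.75, 18 and 36, d = 0.24: Var = 0.435 × (0.1875/18 + 0.2499/36) = 0.00755, SE = 0.0869. Power at 24 points is 78.9%, and the MDE is 24.4 points. The plan's figure of about 24 therefore comes from the linear model at 90% retention.

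**Power at 18% and 22%.** On 75%, these are 13.5 and 16.5 points. With 18 and 36:

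| Model | MDE (points) | Power at 18% | Power at 22% |
|---|---|---|---|
| Scaled from the stated MDE, Φ(2.80 × d/24 − 1.96) | 24 | 35% | 49% |
| Linear | 24.4 | 35% | 48% |
| Constant, baseline-adjusted | 20.0 | 48% | 64% |
| Constant, unadjusted | 26.0 | 31% | 43% |
| Constant, baseline difference subtracted | 28.5 | 27% | 37% |

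**Most favourable case.** 78% placebo positivity, all 60 evaluable, constant baseline-adjusted effect, 22% reduction: about 74%. With 18 and 36, 80% power at a 22% reduction would need a placebo rate of about 83% (constant, adjusted) or 89% (linear). Both lie outside the 72-78% that the plan's figures allow.

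**The 14.5-point patch figure.** With 16 and 32, it needs an assumed reference rate of about 97% (linear) or 93% (constant, adjusted). No patch rate is given. At the urine-implied 75% and 80% retention, the MDE is 25.8 points (linear) or 21.2 (constant, adjusted). The smaller MDE is also paired with the lower retention, the reverse of what a single outcome would give.

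**The case against.** The strongest objection is that the opening paragraph of 11.3 does not say whether 18-22% is relative. That paragraph assumes a constant effect, and the constant, baseline-adjusted MDE is 20 points, in the middle of 18-22. Read as percentage points, power would be 72-87% under that model. But under the linear model actually specified it would be 55-72%, and both ends of the range lie below the stated 24-point MDE. The risk ratios in 8.5 and the matching wording in 8.13 also point to the relative reading. The objection lowers certainty about what was meant, but 80% across the range is not delivered either way.

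Three qualifications stand. The 75% placebo rate is back-calculated from two rounded figures. The 48-64% requires baseline adjustment; other constant-effect analyses give less. The pilot's subgroup result concerned meth-using days, so turning 22% into points of urine positivity assumes the same relative effect on both measures.

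It can also be said that this is a drafting splice: the 24-point figure is consistent between 11.3 and the SAP and reproduces, and the SAP makes no 18-22% claim. That is fair, and it is why the remedy is small. The patch figure is a separate mismatch of outcome, unsupported rather than shown to be miscalculated.

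**Conclusion.** The concern holds; the power claim in 11.3 is wrong as written and must be corrected. Against a stated 80%, power at an 18-22% relative reduction is about 35-49% under the plan's linear model and 48-64% under a constant, baseline-adjusted effect. No variant consistent with the plan's figures exceeds about 74%. These numbers rest on the derived 75% placebo positivity, correlation 0.45, and 36 and 18 retained (all 60 evaluable for the 74%). The contradiction itself needs none of these, since 18-22% is below 32%.

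Nothing here says the pilot effect is the right target. The pilot ran 8 weeks without the momentary intervention. Only the power stated for that effect is at fault.

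**What to change.** 1. Delete the statement of 80% power for 18-22% in 11.3.
2. Settle one outcome (urine, also correcting the sweat patch wording of Aim 1 in 11.3), one effect shape (constant or linear), one retention figure (80% or 90%) and one N convention (60 enrolled; 54 is 90% of 60).
3. Have the study statistician recompute one urine MDE on those choices, with the assumed placebo positivity stated, and give it identically in 8.13, 11.3 and the SAP. It replaces the 14.5-point patch figure. As a check, the linear model gives about 24 points (32%) at 90% retention and about 26 points at 80%.
4. Replace the claim of similar earlier reductions in 11.3 and the SAP with the pilot's 18% (intention to treat, not significant) and 22% (subgroup, meth-using days). State the power at those effects under the chosen model: about 35-49% if linear with the stated MDE, about 48-64% if constant with baseline adjustment.

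The cost is one recalculation and wording changes in three places. The stated power becomes less favourable; no additional patients are needed.

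### Protocol 11.3 ties its detectable effects to an immediate, roughly constant effect, but the Aim 1 model makes the effect grow linearly to week 12; the plan should say which shape and baseline handling the 80% power refers to

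*Protocol*

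**What the plan says.** The opening of Protocol 11.3 hypothesises that oral naltrexone reaches full efficacy almost immediately; "accordingly we expect treatment-control differences to be approximately constant over the 12 weeks of the trial". After a sentence on retention it continues: "Under these assumptions, the minimum detectable effects for our outcomes are calculated as follows".

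The Specific Aim 1 text directly below gives a different shape: "The treatment effect of ION vs. placebo will be modeled as linearly increasing and summarized by the between-group difference in means at 12 weeks". Protocol 8.13 and SAP Specific Aim 1 specify the same model. On baseline, all three say only that the effect is "summarized by the between-group difference in means at 12 weeks, net of any baseline difference". None says whether baseline urine is an outcome, a covariate or a value to be subtracted, and none lists the model terms or the working correlation.

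The Aim 1 power statement in 11.3 is that "the study sample of 60 participants will have 80% power", in "2-sided tests with a type-I error rate of 5" per cent, to detect "net between-group differences in the reduction in urine positivity of ~24 percentage points, equivalent to a relative rate reduction of 32" per cent. The SAP gives the same effect for 54 participants. The 11.3 lead-in quotes another target, "to detect between a 18-22% reduction of meth use among the ION arm". Neither document plans a constant-effect analysis for Aim 1.

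**The concern.** The primary-aim power claim is introduced under one effect shape and the primary model is built on another. A model that forces the arm difference to start at the baseline gap and grow in a straight line can misread an effect that is complete by week 1: the arm term takes up much of the effect and the slope picks up only the rest. Whether that happens depends on how the week-12 contrast is made net of baseline, which the plan leaves open. A reader therefore cannot tell what the 80% covers. If the choice is made after unblinding, there is also room to select among specifications with very different power.

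**Working it through.** **Inputs from the documents.** Two-sided 5%; 2:1 allocation; 60 enrolled (40:20), 90% retained, so 60 × 0.90 = 54 (36:18); within-subject correlation 0.45; effect 24 points, 32% relative.

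**Assumptions not in the documents.** Reference positivity 24/0.32 = 75%, hence 51% on ION; exchangeable correlation; 13 time points (baseline and weeks 1-12); a normal approximation on the percentage-point scale.

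**Formulas.** SE = √(f × [v₁/n₁ + v₀/n₀]) and MDE = (1.960 + 0.842) × SE. The placebo variance is v₀ = 0.75 × 0.25 = 0.1875. For v₁, I use 0.1875 (common variance) and 0.51 × 0.49 = 0.2499 (arm-specific). At 36:18 the bracket is 0.01563 or 0.01736; at 40:20 it is 0.01406 or 0.01562. The factor f depends on the contrast.

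**Step 1: the plan's figure under linear growth.** Model arm + week + arm × week, baseline as an outcome, weeks 0-12, Σ(t − 6)² = 182.

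f = 0.55 × 12²/182 = 0.435.

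- 36:18: SE 8.25 to 8.69 points; MDE 23.1 to 24.3; power at 24 points 83% to 79%.
- 40:20: SE 7.82 to 8.25; MDE 21.9 to 23.1; power 87% to 83%.

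**Step 2: the plan's figure under a constant effect.** Arm difference in the weeks 1-12 average, baseline not used.

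f = (1 + 11 × 0.45)/12 = 0.496.

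- 36:18: SE 8.80 to 9.28; MDE 24.7 to 26.0; power 78% to 73%.
- 40:20: SE 8.35 to 8.80; MDE 23.4 to 24.7; power 82% to 78%.

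The linear model fits the stated figure better at 54 and the constant-effect average fits at least as well at 60. The figure does not identify the shape.

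**Step 3: constant truth, linear model, baseline as an outcome.** Let the arm difference be 0 at week 0 and d at weeks 1-12. The least-squares slope is Σ(t − 6)D(t)/182 = 6d/182. Over 12 weeks this gives 72d/182 = 0.396d, so 24 points is estimated as 9.5.

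- 36:18: 9.5/8.25 = 1.15 and 9.5/8.69 = 1.09, so power is 21% and 19%.
- 40:20: 9.5/7.82 = 1.21 and 9.5/8.25 = 1.15, so power is 23% and 21%.

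Simulated Poisson GEE with robust standard errors gave roughly 23-30% power and a median risk ratio near 0.83 against a true 0.68.

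**Step 4: baseline urine as a covariate.** Fit arm, week and arm × week to weeks 1-12 and test the fitted week-12 difference. The mean week is 6.5 and Σ(t − 6.5)² = 143.

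f = 0.55 × (1/12 + 5.5²/143) + 0.45 − 0.45² = 0.410.

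- 36:18: SE 8.00 to 8.43; power 85% to 81%.
- 40:20: SE 7.59 to 8.00; power 88% to 85%.

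A constant difference and a linearly growing one both lie inside this model, so the week-12 value is recovered under either. Simulation gave 80-83%.

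**Step 5: subtracting observed baseline from the fitted week-12 value.** f = 0.55 × (1/12 + 5.5²/143) + 0.45 + 1 − 2 × 0.45 = 0.712. With common variance the SE is 10.55 at 36:18 and 10.01 at 40:20, and power is 62% and 67% under either shape.

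**The case against.** Three points can be made for the plan.

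First, the analysis is stated the same way in three places, and the SAP contains no constant-effect sentence. Only a rationale in the Protocol disagrees. This stands, and it limits the seriousness: SAP Aim 1 is coherent in itself.

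Second, the assumptions behind the MDEs may be only retention and correlation. The Aim 1 text repeats the phrase about assumptions straight after giving those two values, and in the lead-in the nearest sentence is also about retention. That reading is possible. It would leave the effect-shape sentence in the sample-size justification with no role, still opposed to the model that follows.

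Third, the low-power figure is conditional. It needs an effect complete by week 1, separate arm intercepts and baseline as an outcome. It also assumes flat 75% positivity, although Protocol 11.7 requires a positive sweat-patch or urine sample at screening, so positivity could fall after entry in both arms. The condition on the model stands. The flat rate matters less: the fraction 72/182 concerns only the difference between arms, so on the percentage-point scale a fall shared by both arms alters the variance but not that fraction.

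A reader might infer that the constant-effect sentence is the leftover, since linear growth reproduces about 24 points and the lead-in's 18-22% differs from the 32% below it. The documents do not support that. At the Protocol's 60 participants a constant-effect average gives an MDE of 23.4-24.7, against 21.9-23.1 for linear growth. Either sentence may be the stale one.

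**Conclusion.** The contradiction is in the current text and is unreconciled: the 11.3 lead-in expects a constant effect, and the Aim 1 model in Protocol 8.13, Protocol 11.3 and the SAP specifies a linearly increasing one. Under the lead-in's own hypothesis, the 80% at about 24 points fails on one natural reading of the model (about 19-23% power, estimate near 9.5 points). It survives on another (about 80-88% with baseline as a covariate). The plan does not say which applies.

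It would be too strong to say that the trial has only 20% power. That holds for one combination of true effect shape and model terms, and the documents commit to neither. All sizes rest on the back-calculated 75%, exchangeable correlation and 13 time points. The separate figure of about 14.5 points in Protocol 8.13 is not assessed here.

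This should be fixed; it does not show that the primary analysis is wrong.

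**What to change.** Before unblinding:

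1. Reconcile the effect-shape sentence in the 11.3 lead-in with the Aim 1 model in Protocol 8.13, Protocol 11.3 and the SAP, and state which shape underlies the MDE.
2. State the model terms, the handling of baseline urine (outcome, covariate or subtraction) and the working correlation in both documents.
3. Restate the 80% and about 24 points for exactly that contrast and sample size.

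If arm + week + arm × week with baseline as an outcome is kept, say that the 80% applies only to an effect growing linearly to week 12, and that power for a constant effect of the same size is about 20%. Using baseline urine as a covariate avoids this loss.

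The cost is one corrected sentence in 11.3, a restated power sentence and one or two sentences on model terms. Sample size, visits and data collection do not change.

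A constant-effect risk ratio over weeks 1-12 is optional and supporting only. At 36:18 its MDE would be about 19-20 points if baseline-adjusted (f = 0.496 − 0.45² = 0.293) and 25-26 if not. It is a trade-off: if the effect in fact builds linearly to a risk ratio of 0.68, simulated power for that analysis is about 27-48%.
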